6.3 Dosing and Administration

Details for Trial Intervention (Test Group):

- Timing of Intervention: Participants can log in at their convenience, with the flexibility to schedule exercise coaching sessions according to their preferences and availability.
- Intervention Structure: Over the course of 12-months or 48 weeks, each participant will participate in 3-5 weekly live sessions. Each session, spanning approximately 45 minutes, combines 30 minutes of targeted exercise with 7 minutes of meditation. Each session will be supervised live by a coactive coach for each participant. The program is strategically developed to progressively escalate in intensity:
 - Each session will consist of an optimal combination of Aerobic and Strength exercises.
 - Flexibility and Balance exercises will be included as supplemental exercises in the sessions.

12 Months Program Structure

Months 1 and 2

- Initially participants will be given 1:1 coaching to ensure that the participants get immediate feedback as well as modifications as needed.
- 10 workouts will be presented to the participants in Month 1 and 2. Each workout will be repeated 4 times, hence completing 40 days of workouts.
- The first 2 weeks will be “Light”: allowing the participants to complete the 10 workouts in flow while building confidence without pushing too hard or feeling too sore.
- The second 2 weeks will be “Light/Moderate”: allowing the participant to repeat the same 10 workouts, feel more confident in their ability to finish each workout because they are not brand new, but also experience a slight challenge on the body with the order in which the workouts are laid out.
- The third 2 weeks will be “Moderate”: the participants are expected to begin to feel stronger and more capable at this point which allows them to push a little harder and enjoy the challenge without burnout.
- The fourth 2 weeks will be “Moderate/Hard”: the participant by now should be experiencing what it’s like for the body to master the foundational goals above.

Month 3, 4, 5 and 6

- Next set of 10 workouts will be introduced in months 3 and 4, and likewise in months 5 and 6.

Month 6 to 12

- Based on their ability and progress, participants will be slowly graduated from 1:1 coactive sessions to Group-coactive sessions.

- Planned Route of Administration: The intervention will be administered remotely via the online platform, accessible through mobile devices.

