6.7 Trial Intervention Compliance

Measures will be employed to ensure and document trial intervention compliance.

- Participant Engagement Metrics: The software platform will be equipped with tracking features to monitor participant engagement. Key metrics may include:
 - Frequency of logins and sessions attended.
 - Duration of each coaching session.
 - Participation in interactive features such as progress tracking and sharing exercise exertion feedback.
- Participant Surveys or Feedback: Program feedback for the intervention will be collected after each session.
- Attendance Records: For live Coactive coaching sessions, attendance records will be maintained to track participant involvement and compliance with scheduled sessions.
- System Logs: The software will generate system logs capturing user activity, such as login times, session durations, and interactions within the software. These logs serve as objective documentation of participant engagement.

Mandatory documents to complete include:

- Patient Reported Outcomes: These outcomes include all primary, secondary and exploratory metrics as highlighted above.
- Participant Engagement Logs: These logs will capture key metrics related to participant engagement and compliance with the software and coaching.
- Attendance Records: Specifically for live coaching sessions, attendance records will document participant attendance and participation.

Source data and records used to document trial intervention compliance will include:

- Digital Platform Data: System logs and engagement metrics generated by the software.
- Participant Surveys/Feedback: Responses collected from participant surveys or feedback forms.
- Attendance Records: Records of participant attendance at live coaching sessions.

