9.2 Analyses Supporting Primary Objective(s)

The primary analysis will focus on quantifying the impact of **Complement Theory on changes in Quality of Life Score (QoLS), measured by the FACT-G instrument**, over the trial period. Assessments will occur at baseline, 3, 6, 9, 12, and 18 months.

- **Statistical Model, Hypothesis, and Method of Analysis**

- Primary Estimand (Change in QoLS):
 - Null Hypothesis (H0): There is no difference in the mean change in FACT-G QoLS between participants in the Complement Theory program and those in the control group at specified time points.
 - Alternative Hypothesis (H1): Participants in the Complement Theory program demonstrate a statistically significant improvement in QoLS compared to the control group.
- Baseline Data Analysis: Baseline demographics and characteristics will be provided and summarized in both treatment and control groups. Standardized mean differences (SMDs) will be calculated as the measure of distance between groups. SMDs of 0.2 to <0.5, 0.5 to <0.8 and ≥0.8 are considered small, medium, and large, respectively. Frequencies and percentage will be provided for the binary variables as well as the categorical variables (Yes/No); mean (standard deviation) and median (range) will be computed for continuous variables.
- Method of Analysis: Mixed models for repeated measures (MMRM) will be utilized to analyze changes in FACT-G scores over time, accounting for within-subject correlations. This model allows for the inclusion of both fixed effects and random effects to account for individual variability. In addition, covariate-time interaction terms will be included to guarantee the best results. The strength of the effect from each covariate will be evaluated

through the statistical test significance, i.e., P value, at 95% confidence interval.

- **Handling of Intercurrent Events of Primary Estimand(s)**

- For participants who discontinue the intervention or are non-adherent, we will employ a treatment policy strategy. This means all data collected will be analyzed as per the initial treatment assignment, regardless of the discontinuation or level of adherence, preserving the intention-to-treat principle.

- **Handling of Missing Data**

- Given the potential for missing QoLS data due to dropout or non-response, a multiple imputation (MI) approach will be adopted. The imputation model will incorporate variables predictive of missingness and outcomes to generate plausible values for missing data.

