9.7 Sample Size Determination

- The metric-wise sample size calculation is provided in the table below on alpha as 0.05 and power of 80% for the one-tail test at enrollment ratio = 1.
- While we are conducting the power analysis and sample size calculation based on several variables (outcomes) of interest, the sample size was computed separately for each parameter in the study and the greatest is used to obtain sample size.
- The analysis (detailed below in table) showed that sample of size of 102 is powerful enough for the analysis to cover 100% of primary and secondary metrics.
- Now since we believe that the long follow-up duration of 6 months for our trial will lead to around 30% drop-offs, we decided a final sample size of 146 (73 control, 73 test).

- So even if get 30% or 44 participants drop off we end up with final sample set of 102 (51 control, 51 test) and would be able to come to statistically significant effects ($p < 0.05$) with respect to 100% of primary and secondary metrics.

Metric Segment	Sub Metric	Control Data	Test Data	Assumed Variance	Sample Size
Primary Outcome / Concerns					
Quality of Life Improvement	QoLS Score (FACT-G)	70	85	Variance of 20	42 (21 Control, 21 Test)
Secondary Outcome / Concerns					
Presenteeism	Attitude towards work	2	4	Variance of 1.5	16 (8 Control, 8 Test)
	Employee Performance	0.6	0.7	Variance of 20%	102 (51 Control, 51 Test)
Absenteeism	Working Hours	30	40	Variance of 10	28 (14 Control, 14 Test)
	Vacation Days	0.5	0.3	Variance of 0.15	16 (8 Control, 8 Test)
Exploratory Outcomes					
Cancer Care	Cancer Progression Status	0.85	0.88	Variance of 0.04	46 (23 Control, 23 Test)

	Cancer recurrence status	0.3	0.21	Variance of 10%	32 (16 Control, 16 Test)
Medical Expenditure	Total Healthcare Expenditure (Planned + Unplanned)	10000	8000	Variance of 4000	102 (51 Control, 51 Test)
	No of Urgent Care Visits	3	2.5	Variance of 0.5	28 (14 Control, 14 Test)
	No of ED Visits	5	3.45	Variance of 0.8	10 (5 Control, 5 Test)
	No of unplanned outpatient/office visits (other than ED)	4.28	3.5	Variance of 0.8	28 (14 Control, 14 Test)
	Unplanned Hospitalisations	5	4	Variance of 0.8	18 (9 Control, 9 Test)
	Length of hospital stay	3	2	Variance of 0.8	18 (9 Control, 9 Test)
	No of planned outpatient visits	2	1.8	Variance of 0.3	58 (29 Control, 29 Test)
	No of planned hospital visits	1.25	1	Variance of 0.1	10 (5 Control, 5 Test)
	Length of hospital stay	3	2	Variance of 0.8	18 (9 Control, 9 Test)

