6.3 Dosing and Administration

Details for Trial Intervention (Test Group):

- Timing of Intervention: Participants can log in at their convenience, with the flexibility to schedule exercise coaching sessions according to their preferences and availability.
- Intervention Structure: Over the course of 24 weeks, each participant will participate in 3-5 weekly live one-on-one sessions. Each session, spanning

approximately 45 minutes, combines 30 minutes of targeted exercise with 7 minutes of meditation. Each session will be supervised live by a coach 1:1 for each participant. The coach will be able to ensure that the participants get immediate feedback as well as modifications as needed. The program is strategically developed to progressively escalate in intensity:

- Each session will consist of an optimal combination of Aerobic and Strength exercises.
- Flexibility and Balance exercises will be included as supplemental exercises in the sessions.

6 Months Program Structure

Months 1 and 2

- 10 workouts will be presented to the participants in Month 1 and 2. Each workout will be repeated 4 times, hence completing 40 days of workouts.
- The first 2 weeks will be “Light”: allowing the participants to complete the 10 workouts in flow while building confidence without pushing too hard or feeling too sore.
- The second 2 weeks will be “Light/Moderate”: allowing the participant to repeat the same 10 workouts, feel more confident in their ability to finish each workout because they are not brand new, but also experience a slight challenge on the body with the order in which the workouts are laid out.
- The third 2 weeks will be “Moderate”: the participants are expected to begin to feel stronger and more capable at this point which allows them to push a little harder and enjoy the challenge without burnout.

- The fourth 2 weeks will be “Moderate/Hard”: the participant by now should be experiencing what it’s like for the body to master the foundational goals above.

Month 3, 4, 5 and 6

- Next set of 10 workouts will be introduced in months 3 and 4, and likewise in months 5 and 6.

- Planned Route of Administration: The intervention will be administered remotely via the online platform, accessible through mobile devices.

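### Live coaches and group sessions exist only in the test arm, but no planned model has a coach or group term, so the standard error will be too small if coaches or groups differ in effect.

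*Protocol*

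**What the plan says.** Protocol section 6.3 has every test-arm session supervised live by a coach. Coaching is one-to-one at first. For months 6 to 12 it states: "Based on their ability and progress, participants will be slowly graduated from 1:1 coactive sessions to Group-coactive sessions". Under the dose-modification heading, intensity and frequency are adjusted as the coach guides, with no predefined criteria. Section 4.1 gives controls an app without live coaching or personalization.

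Section 9.2 analyses FACT-G by a mixed model for repeated measures, "accounting for within-subject correlations. This model allows for the inclusion of both fixed effects and random effects to account for individual variability". Section 9.3 uses a Poisson model for leave days and mixed-effects models for the presenteeism scores. None of these, nor the imputation or sensitivity analyses, mentions coach or group.

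Section 9.7 sizes the trial on "alpha as 0.05 and power of 80% for the one-tail test at enrollment ratio = 1". It contains no ICC or design effect. Section 6.7 says "attendance records will be maintained to track participant involvement", but does not say that coach or group identity is stored.

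The Combined protocol and SAP describes a 24-week programme of one-to-one coaching only: "Each session will be supervised live by a coach 1:1 for each participant". The group element therefore rests on the Protocol alone.

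**The concern.** This is a partially nested design: test-arm participants may be clustered by coach, and later by group, while each control stands alone. Outcomes of people who share a coach can be correlated, because coaches differ in skill and, here, in how they set intensity. Random effects for individual variability absorb correlation between visits of one person, not between persons. Left out, the cluster component makes the test-arm variance too small, the confidence interval too narrow and the P value too low.

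Section 2.1 says the trial is meant to isolate the effect of coaching and personalization. With few coaches, part of an apparent programme effect could belong to the particular coaches employed. The group sequential boundaries in 9.6 also hold their error rate only if the variance of the test statistic is right.

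**Working it through.** **The plan's own figures (Protocol 9.7).** The spread column is headed as a variance, but the figures work only if it is read as a standard deviation (SD).

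- FACT-G row: "70 85 Variance of 20". Per arm, n = 2(1.645 + 0.842)² × 20² / 15² = 22, or 44 in total, against the stated "42 (21 Control, 21 Test" patients. A true variance of 20 would give 2 per arm.
- Employee Performance row: difference 0.1, SD 0.2, one-sided t-test. This gives 51 per arm, or 102, and 102 / 0.70 = 146.

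The totals reproduce, to within 2 patients for FACT-G, with no clustering allowance.

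**Are coaches shared?** In a group session, yes, by definition. In the one-to-one phase this is inferred. With all 73 test-arm participants active at 3 to 5 sessions a week, 219 to 365 sessions are needed, and at 45 minutes each that is about 164 to 274 hours. If a coach delivers 25 to 40 live hours a week (assumption), about 4 to 11 coaches carry about 7 to 18 participants each.

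**Effect on the standard error.** Assume m participants per coach, equal arms and equal total variance in both arms.

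- Test-arm design effect: DE = 1 + (m − 1) × ICC. Control arm: 1.
- Ratio of true to model standard error: r = √((1 + DE)/2).
- Actual two-sided error: 2[1 − Φ(1.960/r)]. One-sided: 1 − Φ(1.645/r).

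| m | ICC | DE | r | Model SE too small by (1 − 1/r) | Two-sided | One-sided |
|---|---|---|---|---|---|---|
| 5 | 0.02 | 1.08 | 1.020 | 1.9% | 5.5% | 5.3% |
| 10 | 0.01 | 1.09 | 1.022 | 2.1% | 5.5% | 5.4% |
| 10 | 0.05 | 1.45 | 1.107 | 9.7% | 7.7% | 6.9% |
| 15 | 0.10 | 2.40 | 1.304 | 23.3% | 13.3% | 10.4% |

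**Simulation check.** With 40,000 trials of 5 coaches × 10 participants against 51 controls, a two-sided test that ignores coach rejects in about 5.0% at ICC 0, 5.3% at ICC 0.01 and 7.5 to 7.8% at ICC 0.05 (across runs). A coach-level test with Satterthwaite degrees of freedom stays near 5.4% at ICC 0.05. Its average confidence interval is about 7% wider than the unadjusted one when coaches do not differ, and about 21% wider at ICC 0.05.

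**Effect on FACT-G power.** With a 15-point difference, SD 20, 51 per arm and a one-sided 5% test, power with the corrected standard error is 0.98 at the mild end of the range (m = 5, ICC 0.02) and 0.90 at the severe end (m = 15, ICC 0.10). It is 0.82 even at m = 25 and ICC 0.10. These are normal approximations, without the further loss from few degrees of freedom.

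**The case against.** The strongest reply is that nothing in the documents shows that coaches differ, how many participants each carries, or that a participant keeps one coach. Coaches receive standardized training with refreshers (section 8). At an ICC near 0.01 and these caseloads the error rate hardly moves. This stands, and it is why the point is conditional. A reader might infer that the standard error is certainly too small and that false positives certainly exceed 5%. The documents do not support that. Training may reduce coach differences, but it does not put any remaining difference into the standard error.

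A second tempting reading is that the cure is a random effect for the group attended. That is unsound as a primary analysis, because graduation depends on ability and progress after randomisation. Participants sorted by prognosis look alike within groups without any group effect. In simulation with no true cluster effect and five groups of 10 sorted by prognosis, the unadjusted test holds 5%. A group-level test falls to about 2% at a prognosis-outcome correlation of 0.3, with an interval about 35% wider.

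Third, section 6.3 lets participants schedule sessions to suit themselves, so they may rotate between coaches. With full rotation over five coaches and coach variance at 5% of the total, the unadjusted test and a test with one assigned coach per participant both run at about 8%. One coach code per person is then not enough.

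Finally, group sessions cannot affect FACT-G at 3 months and hardly at 6 months. Those visits can carry coach clustering only.

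**Conclusion.** The gap in the analysis is real: a possible source of correlation, present in one arm only, is in none of the planned models. Its consequence is conditional. For any positive ICC with shared coaches or groups, the error is toward declaring a difference.

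The range of 5.5 to 13% two-sided (5.3 to 10% one-sided) rests on an assumed 5 to 15 participants per coach, an assumed ICC of 0.02 to 0.10, and coach sharing that is inferred for the one-to-one phase. Since 9.7 is one-tailed, the one-sided figures apply if the final test is too. The upper ratio of 1.30 should not be read as a model standard error 30% too small: the true value is 30% larger, so the model's is 23% too small.

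The stake for FACT-G is the confidence interval and the error rate. Power under the assumed 15-point effect stays at about 0.8 or above, so no larger sample is needed for the primary endpoint. The broader claim in 9.7, "sample of size of 102 is powerful enough for the analysis to cover 100% of primary and secondary metrics", has no such margin in the Employee Performance row, which needs all 51 per arm before any clustering.

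**What to change.** 1. Record the coach, and from month 6 the group, for every test-arm session, and carry both into the analysis dataset.
2. In 9.2 and 9.3, prespecify a partially nested model: a coach random effect in the test arm only, each control as a cluster of one, and Kenward-Roger or Satterthwaite degrees of freedom. Use arm-specific residual variances in the models for continuous outcomes.
3. Define the coach term in advance: the main coach of the one-to-one phase or, if participants rotate, multiple membership weighted by sessions. The latter helps only as far as participants' mixes of coaches differ. If all rotate evenly, coach variance cannot be separated, and the report should say so.
4. Use group membership only in a sensitivity analysis.
5. Report the number of coaches, the caseloads and the estimated ICC.

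The cost is one or two data fields, SAP wording and a wider interval: about 7% wider with five coaches who do not differ, and about 20% at ICC 0.05. Recording should start before sessions accrue, because coach identity may be hard to reconstruct afterwards.

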6.4 Treatment of Overdose

While overdose typically refers to the administration of excessive doses of pharmacological agents, in the case of a software solution, it pertains to the potential for participants to overexert themselves during exercise sessions, leading to adverse effects

such as muscle strains, joint injuries, fatigue, or exacerbation of underlying health conditions.

Given the nature of the trial intervention, there are no specific antidotes or therapies for trial intervention overdose. However, measures will be in place to prevent and manage potential adverse events associated with excessive exercise. These measures include:

- Individualized Exercise Prescription: The software app provides personalized exercise coaching tailored to each participant's fitness level, health status, and exercise tolerance through an intake form. Each patient is categorized into low or moderate based on the form. Exercise sessions will be designed to gradually progress in intensity and duration for each individual based on participants' responses and feedback.
- Monitoring and Supervision: Participants will be closely monitored during exercise sessions by trained exercise coaches who can provide real-time feedback and guidance. Coaches will ensure that participants adhere to safe exercise practices and modify activities as needed to prevent overexertion or injury. The survivor will be filling a RPE (Rating of Perceived Exertion) form after each session and will be given feedback based on the same.
- Participant Education: Participants will receive education and instruction on proper exercise techniques, warm-up and cool-down procedures, and signs of overexertion or injury. They will be encouraged to listen to their bodies and communicate any discomfort or concerns to their exercise coach.
- Flexibility and Adaptability: The solution app offers flexibility in scheduling and adapting exercise sessions to accommodate participants' individual preferences, capabilities, and constraints. Participants have the autonomy to adjust the intensity or duration of exercises based on their comfort level and feedback from the exercise coach.
- Prompt Recognition and Response: In the event of symptoms suggestive of overexertion or adverse effects during exercise sessions, participants will be

instructed to stop the activity immediately and seek appropriate medical attention if necessary. Coaches will be trained to recognize signs of overexertion and intervene promptly to ensure participant safety.

6.5 Preparation, Handling, Storage and Accountability

- **Preparation of Trial Intervention**

- For both the trial intervention and control product, there are no specific preparation or administration procedures beyond accessing the online platform and following the instructions provided therein. These procedures are straightforward and do not require any specialized preparation or handling by trial personnel.

- **Accountability of Trial Intervention**

- Distribution of Trial Intervention:
 - The trial intervention will be distributed to participants electronically. Upon enrollment in the trial, participants will receive login credentials and instructions for accessing the digital platform via email or through a secure online portal.
 - Distribution of the trial intervention will be managed by the study coordinators or research personnel responsible for participant enrollment and communication. They will ensure that participants receive the necessary information and support to access the digital platform and engage in exercise coaching sessions.

- **Expectations for Reconciliation:**

- Reconciliation of the trial intervention will involve tracking participant engagement and adherence to the software app through the online platform. Study coordinators or research personnel will monitor participant activity logs and session completion rates to ensure compliance with the trial protocol.
 - Any discrepancies or issues related to participant access or engagement with the digital platform will be documented and

addressed promptly to maintain data integrity and participant accountability.

